6.5 Data presentations

The TFLs will present treatment group (i.e. tideglusib or placebo).

TFLs on the PKAS, SAF and FAS analysis sets will be presented according to the treatment actually received (i.e. tideglusib or placebo), regardless of the randomization.

TFLs on the Enrolled, ITT and PPS analysis sets will be presented according to the randomized treatment group.

The data will be summarised in tabular form by treatment group apart from disposition of subjects, protocol deviations and background and demographic data which will be summarised by treatment group and overall subjects.

Only scheduled post-baseline laboratory, vital signs and ECG values will be tabulated, post-baseline repeat/unscheduled assessments will be listed only; all clinically significant values will be noted.

Individual subject assignments to each analysis set will be summarized using the Enrolled set. The primary and key secondary efficacy endpoints will be summarised using the ITT and the PPS. All other secondary endpoints will be summarised using the ITT. PK concentration data will be summarised using the PKAS set and all other data will be summarized using the SAF set. Additionally, run-in data for efficacy and adverse events will be summarised for the RIS set.

Eligibility, completion/withdrawal, consent/assent, analysis set, protocol deviations, demographic and other background listings in section 6.8 and visit dates will be based on the enrolled set, PK listings will be based on the PKAS set, efficacy listings, run-in treatment, study drug dispensing and return, study drug daily dosing and meal intake data, all adverse events and adverse events leading to death will be based on the RIS set and all other listings will be based on the SAF set. Listings based on

the RIS will presented according to the randomized treatment for the efficacy listings and actual treatment received otherwise.

Graphical presentations of the data will also be provided where appropriate. Unless otherwise stated, only data from Visit onwards will be presented graphically.

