14. Females of child-bearing potential who are pregnant, lactating or not willing to use a protocol-defined acceptable contraception*** method if sexually active and not surgically sterile

- 15. Males, engaged in sexual relations with a female of child-bearing potential, not using an acceptable contraceptive*** method if not surgically sterile
- 16. Kidney disease requiring ongoing treatment
- 17. A history of chronic liver disease with current out of range values for ALT, clinically relevant hepatic steatosis or other clinical manifestations of liver disease
- 18. ALT value > 2X the upper limit of the normal reference range at repeat to confirm) (may
- 19. Total bilir bin value greater than the upper limit of the normal reference range at (unless due to Gilbert's syndrome) (may repeat to confirm). For subjects with a well known/well documented diagnosis of Gilbert's syndrome a total bilirubin value greater than 2 x the upper limit of the normal reference range at repeat to confirm) (may repeat to confirm)
- 20. HbA1c values greater than 6% or 42.0 mmol/mol at (may repeat to confirm)
- 21. TSH values outside of the normal reference range at (may repeat to confirm)
- 22. Serum creatinine >1.7 mg/dL (>150 micromole/L or creatinine clearance ≤ 60 mL/min (according to Cockcroft-Gault formula) at the confirm (may repeat to confirm)
- 23. Clinical history of hepatitis or previous or current positive serological evidence for Hepatitis B or C
- 24.24. Serological evidence of Hepatitis A at proceeding or in the preceding
 - 25. A history of significant drug allergy (such as Steven-Johnson syndrome, anaphylaxis)
 - 26. A history of alcohol or substance use disorders
 - 27. Current malignancy or any history of malignancy except for surgically cured skin cancer or pilomatricoma (benign tumor of the hair follicle that is associated with Congenital DM1)
 - 28. Severe arthritis or other medical condition (besides Congenital DM1) that would significantly impact ambulation or completion of myometric assessments
 - 29. Hypersensitivity to tideglusib or any components of its formulation including allergy to strawberry
 - 30. Unable to swallow liquids or may have trouble swallowing liquids (in the opinion of the investigator), unless medication to be administered by gastrostomy tube
 - 31. Judged clinically to be at risk of suicide (suicidal ideation, severe depression, or other factors) over the last three months, as assessed by the investigator.

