10.2.7 Clinical Laboratory Evaluations

All clinical laboratory assays will be performed according to the study laboratory's normal procedures. Reference ranges will be supplied by the study laboratory and will be used to assess the laboratory data for clinical significance and out of range changes.

Safety laboratory and urinalysis samples will be collected remotely in the subject's home using an AMO approved home healthcare vendor for unscheduled visits as required or if required due to a COVID-19 related reason.

[figure not shown]
Biochemistry

A biochemistry sample will be collected as outlined in the schedule of events. Biochemistry blood samples can be drawn with the subject in either a fasting or non-fasting state. However, if a sample needs to be repeated, the subsequent sample should be drawn from the subject in the same fasting/non-fasting state.

AMO Pharma Ltd.

is obtained indicating an active Hepatitis C infection, the result will need to be confirmed and an additional blood sample may be collected from the subject.

Urinalysis

Urinalysis will be performed by dipstick and documented in source documents as outlined in the schedule of events. Abnormal results should be investigated further by sending to the study central laboratory.

Pregnancy Test

Serum pregnancy test for female subjects of child bearing potential at Screening will be performed. At subsequent visits, a urine pregnancy test is sufficient if acceptable and preferable according to local practice. If a female subject of child bearing potential is seen at home for a visit, due to a COVID-19 related reason or an unscheduled visit requiring a pregnancy test, by a home health care professional, the central laboratory will perform a serum pregnancy test using the biochemistry sample.

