- The incidence of Adverse events (AEs), including serious adverse events (SAEs), between Screening and end of treatment. The incidence will also be assessed during a follow-up period after discontinuation of the study drug for those subjects not participating in the extension study AMO-02-MD-2-004.
- The incidence of abnormal findings in objective assessments (e.g. laboratory values, ECGs, vital signs and bone mineral density) between screening and end of treatment. The incidence of abnormal findings in objective assessments will also be assessed during a follow-up period after discontinuation of the study drug for those subjects not participating in the extension study AMO-02-MD-2-004.

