6.17.2 Clinical Laboratory Evaluation

Observed values and change from baseline in and assessments will be summarized over time. At baseline the change from run-in baseline will also be presented. If the test results are reported in categorical format, the results will be summarized by subject counts and percentage for each category.

Each parameter will be classed as low, normal, high based on the reference ranges. Shift tables in relation to the normal range from baseline over time will be presented.

virology and urinalysis data will be listed separately including change from baseline, reference ranges flagging all out of range values and their clinical significance. Separate listings of out of range laboratory measurements recorded throughout the study will be provided. Local laboratory results will be presented on the same listings, where these are collected.

Spaghetti plots of and will be produced containing a separate line for each subject, with the measured value appearing on the y-axis and time (days since first administration of randomized study treatment) on the x-axis. The relevant reference range and 1 x, 2x and 3x Upper Limit of Normal (ULN) will be overlaid on the plot as a reference line.

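### No by-arm count of worst post-baseline laboratory or ECG values is planned: unscheduled results stay out of the tables, and the low/normal/high shift tables cannot show a rise in a child who enters with ALT at 1-2x ULN

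*SAP*

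**What the plan says.** SAP 2.3 (Study Endpoints) makes one safety endpoint "The incidence of abnormal findings in objective assessments (e.g. laboratory values, ECGs, vital signs and bone mineral density") from screening to end of treatment, extended into follow-up for children who do not join the extension study.

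SAP 6.5 (Data presentations) sets the general rule: "Only scheduled post-baseline laboratory, vital signs and ECG values will be tabulated", while "post-baseline repeat/unscheduled assessments will be listed only". The same sentence ends "all clinically significant values will be noted". For baseline the rule differs: SAP 6.3 lets unscheduled assessments count.

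For laboratory data, SAP 6.17.2 says "Each parameter will be classed as low, normal, high based on the reference ranges" and "Shift tables in relation to the normal range from baseline over time will be presented". It also plans by-visit summaries of values and changes, listings of out-of-range results for the whole study (with local results where collected), and subject plots with lines at 1x, 2x and 3x ULN. For ECGs, SAP 6.17.4 (Table 3) counts children in QT/QTc categories over time by timepoint.

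Off-schedule results are expected. Protocol 8.3 calls the visits under section 9.5 unscheduled, 9.5 requires repeat laboratory work when an individual stopping rule is met, and 10.2.7 provides for samples drawn at home by a "home healthcare vendor for unscheduled visits as required". At entry, Protocol 7.3 excludes only "ALT value > 2X the upper limit of the normal reference range", so a child between 1x and 2x ULN can be enrolled (unless there is also a history of chronic liver disease).

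A summary of overall worst post-baseline values appears once, in SAP 6.12, as a possible post hoc addition if the COVID-19 missing-data summaries suggest it.

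**The concern.** An incidence endpoint needs a count of children per arm. The tables that count children by objective laboratory or ECG criteria use scheduled values only, yet the protocol's response to an abnormal result is more testing off schedule. The shift table adds a second gap. A child already above the normal range at baseline sits in the top class, so further worsening has no cell to move to.

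Liver safety is where this matters most. The protocol lists ALT tables from three earlier studies, ALT and liver exclusions, laboratory alerts, and attention to ALT and bilirubin after overdose. At stake is whether the report can state, by arm, how many children crossed a given ALT or QTc threshold at any time on treatment. An omission can only lower such a count, and lowers it more in the arm with more off-schedule peaks.

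**Working it through.** The plan gives no figure of its own on this point, so the check follows a value through each planned output and then sizes one omitted child.

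**1. Where a post-baseline value goes**

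| Planned output | Scheduled value | Unscheduled or repeat value | Number of children by arm? |
|---|---|---|---|
| Laboratory summaries by visit (SAP 6.17.2, statistics in 6.1) | Yes, with maximum and change | No (6.5) | No |
| Laboratory shift table (6.17.2) | Yes, three classes | No (6.5) | Yes, but no rise from a high baseline |
| QT/QTc categories (6.17.4, Table 3) | Yes | No (6.5) | Yes, per timepoint |
| TEAE tables (6.17.1) | If reported as an AE | If reported as an AE | Yes, subject to investigator judgement |
| Laboratory and ECG listings | Yes | Yes | No |
| Subject plots with ULN lines (6.17.2) | Yes | Not stated | No |

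The TEAE tables are the only route by which an unscheduled value enters a by-arm count.

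**2. The shift rule applied to assumed ALT values (multiples of ULN, high = above 1)**

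- Baseline 0.8, unscheduled peak 5, next scheduled value 0.9: tabulated as normal to normal, change 0.9 - 0.8 = +0.1.
- Baseline 1.5, scheduled value 1.8: high to high, change +0.3.
- Baseline 1.5, scheduled value 4: high to high, change +2.5.
- Baseline 1.5, scheduled value 8: high to high, change +6.5.
- Baseline 1.5, unscheduled peak 8, scheduled value 1.6: high to high, change +0.1.

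The last four children fall in the same cell. For the scheduled values of 4 and 8, the maximum and the change from baseline do reveal the rise, but as one extreme per visit and not as a number of children. In the first and last cases no laboratory table shows the peak.

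**3. Weight of one child**

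SAP 3 reports 53 randomized at 1:1, so 26 or 27 per arm (assuming a near-even split and that all were treated).

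- One child moves an arm's incidence by 1/27 = 3.7 to 1/26 = 3.8 percentage points.
- For 0/n, the exact (Clopper-Pearson) 95% upper limit is 1 - 0.025^(1/n): 12.8% for n = 27 and 13.2% for n = 26.
- For 1/n, the upper limit is the 97.5% quantile of Beta(2, n - 1): 19.0% for n = 27 and 19.6% for n = 26.

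These limits show how much one child matters at this sample size. They do not estimate how many children would be missed.

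**The case against.** The strongest reply is that little is hidden. Protocol 10.5.1 and 10.5.6 require clinically significant laboratory, ECG and vital-sign abnormalities to be recorded as AEs whatever the visit type, and SAP 6.17.1 tabulates TEAEs by arm, by system organ class and preferred term. Out-of-range laboratory results are listed for the whole study, and the ECG listings flag QT/QTc of 480 and 500 msec or more and increases of 60 msec or more. The plots use days since first randomized dose, so unscheduled points may well be on them. The DSMC sees unblinded safety data quarterly. Restricting by-visit summaries to scheduled draws is ordinary practice, and a worst-value table gives more chances of a peak to children tested more often.

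Much of this stands. A reader might infer that unscheduled peaks cannot appear in any by-arm incidence; the AE route shows that they can. A reader might also infer that the highest values will mostly be unscheduled. The documents do not support that: an alert may be raised by a scheduled draw, and the stopping-rule return visit includes the end-of-treatment assessments. SAP 6.3 counts the last visit as EOT for children withdrawn by the investigator, so such values may be mapped to EOT. The ECG part is also weaker: Table 3 already uses thresholds, and the visible text of Protocol 10.2.8 prescribes no alert-driven repeat ECG.

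The reply does not supply an objective count. The AE route depends on a judgement of clinical significance, and Protocol 10.5.1 prefers an underlying diagnosis to the laboratory finding, so events may spread over several preferred terms. Listings and plots give no percentage by arm.

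**Conclusion.** The gap is real but limited. As written, the SAP yields no by-arm count of children by worst post-baseline laboratory or ECG value. Unscheduled peaks are counted by arm only through AE reporting, rises from an already high baseline do not register in the shift tables, and the Table 3 counts omit unscheduled ECGs.

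Its size is known only per child: about 3.8 percentage points of an arm's incidence at 26 per arm. A reader might go further and put a number on a downward bias. The documents do not support that. No ALT threshold count is planned that could be biased, and nothing visible indicates how many children would peak only off schedule.

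The conclusion assumes that SAP 6.5 governs the shift tables and Table 3, and that the table shells, a separate document not available here, add no worst-value table. Laboratory parameter names in SAP 6.17.2 are blacked out, so ALT being among those summarised and plotted is also an assumption. This is a cheap improvement to the safety reporting. It does not affect the validity of the trial.

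**What to change.** Keep the scheduled-visit summaries as they are, and turn the worst-case summary that SAP 6.12 leaves optional into a planned analysis:

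- In SAP 6.5 and 6.17.2, add one by-arm table of worst post-baseline ALT over all results (scheduled, repeat, unscheduled and local). Give the number and percentage of children in bands split at 1x, 2x and 3x ULN, the multiples already drawn on the SAP's plots. Cross-classify by baseline band and show the concurrent bilirubin category.
- In SAP 6.17.4, add a worst-post-baseline row to Table 3 that includes unscheduled ECGs.
- Footnote both with the number of tests per arm, because more repeat testing gives more chances to show a peak.

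The cost is some SAP wording, one new table and one added row, all from data already collected. No assessment, visit or clinical rule changes. The remaining weakness is unequal testing between arms, which the footnote discloses but does not remove.

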6.6 Disposition of subjects

The number and percentage of all subjects will be presented overall and by site for the following:

- Enrolled set
- Screening failures including inclusion criteria failed and exclusion criteria met.
- RIS set
- Run-in failures.
- Subjects randomized.
- SAF, ITT, FAS, PPS and PKAS sets.
- Subjects who completed the study.
- Subjects who prematurely discontinued from the study including reason for withdrawal.

The percentage of screening failures will be based on the enrolled set and the percentage of run-in failures will be based on the RIS. Otherwise percentages will be based on the number of subjects randomized.

In addition, total duration, derived as (date of study completion or the date of early study withdrawal - date of first administration of study treatment including +1, and double-blind treatment duration derived as (date of study completion or the date of early study withdrawal - date of first administration of randomized study treatment will be summarized.

Screening failures are defined as subjects who do not take at least and who discontinue the study. Run-in failures are defined as subjects who take a

Subjects who prematurely discontinued from the study due to a reason relating to COVID-19 are identified as either of the following:

- Reason for withdrawal of 'Other' with a corresponding free text reason containing a text version of 'COVID-19'.
- Reason for withdrawal of 'Adverse Event' with a corresponding COVID-19 related AE reported on the AE eCRF page.

The number and percentage of subjects who prematurely discontinued due to either of these definitions will be presented as a reason for withdrawal of 'COVID-19'.

Eligibility for each of the analysis sets and reasons for exclusion will be listed. Eligibility criteria, informed consent and assent, study completion/withdrawal and Visit dates data will be listed.

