7.4 Withdrawal Criteria

A subject should be withdrawn from treatment if they meet the discontinuation criteria in section 9.5. If a subject is discontinued at any time after Run-in the investigator will make every effort to see the subject and complete the EOT visit as soon as possible (ideally within 72 hours) after being discontinued from IMP treatment and then attend the follow-up visit, after final dose.

Subjects may withdraw from the study at any time without stating a reason and without prejudice to further treatment. The Investigator may withdraw a subject from the study and discontinue study treatment and assessments at any time.

CONFIDENTIAL Protocol No: AMO-02-MD-2-003

Product: Tideglusib AMO Pharma Ltd.

Early discontinuation of any subject who has given informed consent to participate will be recorded including the reason for discontinuation. The primary reason for a subject withdrawing prematurely will be selected from the following standard categories of early discontinuations:

• Failed to meet enrollment criteria.

Investigational Medicinal

- Adverse Event: Clinical events occurred or laboratory results are reported that in the medical judgment of the investigator are grounds for discontinuation in the best interests of the subject.
- Withdrawal of Consent: The subject desired to withdraw from further participation in the study. The subject is not obliged to provide any reason for withdrawal of consent, but where a reason is given this will be recorded on the CRF.
- **Protocol Violation:** The subject failed to adhere to the protocol requirements, at the investigator's discretion e.g. the subject requires initiating a medication from the prohibited medications list or is consistently noncompliant with the pre- and post-dose food restrictions
- **Pregnancy:** The subject has either a positive urine or serum pregnancy test during the study.
- Lost to Follow-Up: The subject stopped coming for visits and study personnel were unable to contact the subject or caregiver. Every effort should be made to re-contact the subject prior to declaring a subject as lost to follow-up, which must be at least 3 documented attempts. The 3rd must be in writing and confirmed to have been received (e.g. registered post).
- Other: The subject was terminated for a reason other than those listed above, such as theft or loss of study drugs or termination of study by Sponsor.

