9.4 Duration of Subject Participation

The overall expected duration of subject participation is weeks. Clinic visits will be completed per the schedule of events and visits can be completed across either one or two days as necessary. Participation for individual subjects will consist of up to 4 weeks of an initial Screening period followed by a run-in treatment phase. After this, subjects will be randomized to either weight adjusted 1000 mg tideglusib, or matched placebo, once daily orally for weeks. Subjects randomized to weight adjusted 1000 mg tideglusib will receive the 400 mg weight adjusted dose level of tideglusib for two weeks, and then will advance to the 600 mg weight adjusted dose level for the next two weeks. Thereafter, these subjects will take tideglusib at the weight adjusted 1000 mg dose level for weeks (see Figure 5). All subjects will be followed up for weeks after the end of treatment if they are not participating in the extension study AMO-02-MD-2-004.

AMO Pharma Ltd.

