12. END OF THE STUDY

The end of the study is defined as the last subject's last study assessment, which for this protocol is the final follow-up visit conducted post-treatment for those subjects not proceeding into the extension protocol AMO-02-MD-2-004, or the final study assessment for subjects who do proceed into the extension protocol.

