6.3 General Derivations

This section provides details of general derivations. Derivations specific to the parameter of interest are detailed within the specific SAP section:

Randomized study treatment

Where mentioned in this SAP, "Randomized study treatment" will relate to double-blind study treatment (either tideglusib or placebo). In the case of the SAF, this means the treatment that the subject received rather than the treatment that the subject was randomized to.

The first administration of randomized study medication is defined as the first dose of study medication after the date/time of randomization.

Phase

Phase is defined as a subject's treatment period where:

- Screening Phase: relates to the period ending the day of Visit and dosing commences the next day.
- Run-In Phase: relates to the period starting the day after Visit and ending immediately before the date/time of randomization at Visit
- Double-blind Treatment Phase: relates to the period starting immediately after the date/time of randomization and ending the day of the EOT visit, Visit
- Post-Treatment Phase: relates to the period starting from the day after the EOT visit, Visit

If a visit is split across 2 days, completion of the full study visit is when all assessments on the 2nd day have been completed. Hence the end date of the visit should be used in phase derivations where applicable.

Definition of study day

Throughout this SAP any references to "Visit XX" refer to the pre-specified visits defined in the protocol. Data listings will additionally present study day. Study day will be calculated relative to the first date of administration of randomized study treatment (Study Day 1). There is no Study Day 0. The day before Study Day 1 is Study Day 1.

Definition of baseline and run-in baseline

Baseline is defined as the last non-missing value or mean values, where assessments are made in triplicate such as for ECGs, prior to the subject receiving randomized study treatment. Scheduled and unscheduled assessments will be considered.

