6.11 Administration of Study treatment and Exposure

Date:22FEB2023 Version: Final 2.0 ST/form/010/15

The total amount (mg) of randomized treatment expected to be taken is derived as follows:

Date of last dose of randomized treatment— date of first dose of randomized treatment + 1. Any stideglusib/matched placebo received during should be excluded.

the number of subjects that were

The above derived variables and study drug dispensing, study drug return, study drug and subject diary card information will be listed.

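### SAP 6.6 ends double-blind treatment duration at study completion or withdrawal, so the summary can count days off drug

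*SAP*

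**What the plan says.** SAP 6.6 plans two duration summaries. Total duration starts at the first dose of any study treatment. The second is "double-blind treatment duration derived as (date of study completion or the date of early study withdrawal" less the "date of first administration of randomized study treatment will be summarized". Both have the same end date; only the start differs. The tail of the second formula is cut in the public text, but the end date is legible.

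Elsewhere the SAP closes the treatment period differently:

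- SAP 6.3: "Double-blind Treatment Phase: relates to the period starting immediately after the date/time of randomization and ending the day of the EOT visit". Later time belongs to a separate post-treatment phase.
- SAP 6.11, the exposure section: a day count that begins "Date of last dose of randomized treatment" and subtracts the date of first randomized dose, plus 1.
- SAP 6.17.1: adverse events belong to the double-blind treatment period only if they start before 2 days after randomized treatment is discontinued.

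On what happens after treatment, Protocol 9.4 states: "All subjects will be followed up for weeks after the end of treatment if they are not participating in the extension study" (the number of weeks is blacked out). Protocol 12 makes the last assessment "the final follow-up visit conducted post-treatment for those subjects not proceeding into the extension protocol", "or the final study assessment for subjects who do proceed into the extension protocol". Under Protocol 7.4, a child who stops drug early is to have an EOT visit, ideally within 72 hours, "and then attend the follow-up visit, after final dose".

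The SAP does not define a subject's date of study completion. Nothing visible in the 2024 addendum changes the 6.6 derivation.

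**The concern.** A variable called treatment duration should stop when treatment stops. The one in 6.6 stops when the child leaves the study, and the protocol builds in an off-drug interval before that point for some children. Two children with identical dosing could therefore be given different treatment durations because one entered the extension and the other did not. If the share entering the extension differed between arms, the summary would show a difference in treatment duration that has nothing to do with dosing.

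There is also a problem of reading. The 6.17.1 event window and the 6.6 duration carry almost the same name but cover different periods. Someone who sets the adverse event counts beside the duration table would be matching events and time that do not belong together.

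**Working it through.** The documents state no figure for this duration, so there is nothing to reproduce. The check sets the definitions side by side and then illustrates the size under stated assumptions.

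**1. End dates compared**

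| Place | Quantity | Ends at |
|---|---|---|
| SAP 6.6 | double-blind treatment duration | study completion or early withdrawal |
| SAP 6.3 | double-blind treatment phase | day of the EOT visit |
| SAP 6.11 | day count for randomized treatment | last randomized dose |
| SAP 6.17.1 | double-blind period for adverse events | 2 days after randomized treatment stops |

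Only 6.6 uses an end date that is not tied to treatment or to the EOT visit.

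**2. Where off-drug days can enter**

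- *Early stoppers.* Excess = withdrawal date minus last-dose date. Protocol 7.4 asks for an EOT visit and then a follow-up visit after the last dose, so the withdrawal date can be later than the last dose. This does not depend on how completion is defined for completers.
- *Completers not entering the extension.* Let F be the follow-up in weeks. If completion is the follow-up visit, excess = F. If completion is the EOT visit, excess = 0.
- *Completers entering the extension.* They have no off-drug follow-up in this study, so no excess from this source.

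**3. Illustrative size for completers**

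Assumptions: completion is the follow-up visit, F is 2 or 4 weeks, and the double-blind period T is 12, 20 or 26 weeks. F and T are blacked out, so these values are placeholders.

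Per child in days: 7 × 2 = 14; 7 × 4 = 28.

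Per child relative to T (F/T):

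| T | F = 2 | F = 4 |
|---|---|---|
| 12 | 2/12 = 16.7% | 4/12 = 33.3% |
| 20 | 2/20 = 10.0% | 4/20 = 20.0% |
| 26 | 2/26 = 7.7% | 4/26 = 15.4% |

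Arm mean = p × F, where p is the share not entering the extension (not given). With p = 0.25 and T = 20: 0.25 × 2 = 0.5 week (2.5%) to 0.25 × 4 = 1.0 week (5.0%).

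Spurious difference between arms if p differed by 20 percentage points: 0.20 × 14 = 2.8 days to 0.20 × 28 = 5.6 days. The documents give no sign that p does differ.

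**4. After the change**

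Ending at the last randomized dose removes the follow-up excess F and the early-stopper excess. Ending at the EOT visit removes F for completers but can leave days between last dose and EOT visit for early stoppers. SAP 6.3 also takes EOT as the last visit in the study for children lost to follow-up or withdrawn by the investigator, so the last dose is the cleaner end date.

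**The case against.** The strongest reply is that this line is not the exposure analysis. It sits in the disposition section; exposure has its own section, 6.11, which works from dosing dates. That stands. A reader might infer from 6.6 that exposure itself is overstated, or that the denominator of the safety analysis is inflated. The documents support neither. The dose-date count in 6.11 is untouched, adverse events in 6.17.1 are summarised as numbers of events and subjects, their window is set by discontinuation of treatment, and no rate per unit of exposure appears in the visible text.

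Second, the premise about completers is an inference. Protocol 12 defines the end of the trial, not each child's completion date, and the completers' sensitivity analysis in SAP 6.13.1.1 speaks of completing the study to EOT. This also stands: if completion is recorded as the EOT visit, completers have no excess. It does not answer the early-stopper route, and a text that permits both readings needs a definition.

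Third, text is missing. The 6.6 formula is cut, and 6.11 has lost enough that one cannot say its dosing dates serve only the expected amount; its day count may already be a dosing duration. That is a reason not to claim that a correct duration is absent from the plan. It does not rescue 6.6, because the missing part of that formula comes after the start date and the end date is plain.

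**Conclusion.** Wrong as written, and minor. The end date in SAP 6.6 does not fit the variable's name and disagrees with SAP 6.3 and 6.11. The rule counts off-drug days for any early stopper whose withdrawal date is after the last dose. It does so for completers outside the extension only if completion means their follow-up visit.

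The size is unknown. It would be 14 to 28 days per non-extension completer on the assumption of 2 to 4 weeks of follow-up, and zero for completers if completion is the EOT visit. For early stoppers it depends on individual dates. The consequence is confined to one descriptive summary.

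**What to change.** In SAP 6.6, derive double-blind treatment duration as date of last randomized dose minus date of first randomized dose + 1, in line with 6.11. Keep the version that ends at completion or withdrawal, but label it time on study. State which visit date counts as a subject's study completion, separately for children who do and do not enter the extension.

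The cost is one derivation line and a table label. Both dose dates are already needed for 6.11, so no new data are required. If the table has already been produced, rerun it or add a footnote stating the end date used.
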